4. PARTICIPANT ENTRY

4.1 INCLUSION CRITERIA

A subject will be eligible for inclusion in this study only if all of the following criteria apply at the time of screening:

1. Hospitalised with confirmed COVID-19 infection.
2. Screened within 96 hours of SARs-CoV-2 positive PCR.
3. Age 18 or over
4. Systolic blood pressure between 100 and 180

4.2 EXCLUSION CRITERIA

A subject will not be eligible for inclusion in this study if any of the following criteria apply at the time of screening:

1. Any unrelated clinical condition, which, in the opinion of the investigator, may affect D-dimer during the course of the study, independent of COVID-19 infection, e.g. a subset of cancers and coagulopathies.
2. Concomitant medications which inhibit the action of TRV027 (ARB's).
3. Any clinically significant medical conditions that in the opinion of the investigator would compromise subjects' safety or compliance with study procedures.
4. Any clinical condition which in the opinion of the investigator would compromise the scientific integrity of the study
5. Unwillingness or inability to follow the procedures outlined in the protocol.
6. Subject is pregnant or breastfeeding

4.3 CONSENT OR AGREEMENT FROM CONSULTEE

Patients with Capacity

Consent will be obtained from participants who have capacity. After reading the information and having an opportunity to ask questions, they will be asked to sign the consent form. Once the consent form has been signed, a digital copy will be created using the NHS approved PANDO

app, and the original will be destroyed for infection control purposes. At the time of taking consent, patients will be informed of the possibility that they may lose capacity during the study, and they will be asked to record their wishes on the consent form should this happen.

Patients who are physically unable to sign a consent form (due to the severity of their illness) may consent for themselves provided they can understand the information and verbally express their wishes. Their verbal consent will be witnessed by an observer who is independent of the study and the witness will countersign the consent form.

Patients will be informed that they may lose capacity during the study and will be asked to record their advance wishes regarding continuing enrolment on the consent form.

Patients who lack Capacity

If the patient lacks capacity to give consent due to the severity of their medical condition, then they may be enrolled on the advice of a partner, friend or relative acting as the patient's personal consultee. Consent will then be sought with the patient if and when they recover capacity.

Patients who lack capacity to consent and for whom a personal consultee is not immediately available, may be enrolled on the study provided a nominated consultee can be appointed to advise on their behalf. A nominated consultee may be a treating clinician or professional carer (must be independent of the study). Further advice will be obtained from the patient's personal consultee (or consent will be taken directly from the patient if they recover promptly) at the earliest opportunity.

4.4 WITHDRAWAL CRITERIA

Based on current outcome statistics, many subjects are likely to progress to end organ failure resulting in Intensive Therapy Unit (ITU) admission or death. Admission to ITU is therefore expected and will not result in withdrawal of the subject. Provision for informed consent of participants lacking capacity are specified in **sections 4.3 and 8.2**.

Subjects may withdraw from the study at any point, without giving a reason. If the subject loses capacity, the clinician in charge of their care can elect to withdraw the subject if they deem it clinically appropriate to do so.

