8.2 CONSENT

Consent to enter the study must be sought from each participant only after a full explanation has been given, an approved participant information sheet provided and time allowed for consideration. Signed participant consent should be obtained before initiating any study procedures in patients that are capable of giving consent (refer to section 4.3 for further details). The right of the participant to refuse to participate without giving reasons must be respected. Participants that lack capacity may also be enrolled on the advice of a consultee (see section 4.3).

After the participant has entered the study the clinician remains free to give alternative treatment to that specified in the protocol at any stage if he/she feels it is in the participant's best interest, but the reasons for doing so should be recorded. In these cases the participants remain within the study for the purposes of follow-up and data analysis.

All participants are free to withdraw at any time from the protocol treatment without giving reasons and without prejudicing further treatment.

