2.5 Withdrawal from the study

Patients withdrawn from the study will still be included in the final analysis. Withdrawal can occur at any time according to the following reasons: Patient decision; toxicity, lost to follow-up; Death, or PI decision.

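### Protocol 4.4 lets the treating clinician withdraw a subject who loses capacity without separating stopping the infusion from ending data collection, so outcome-related data loss is possible

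*Protocol*

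**What the plan says.** **Protocol 4.4** expects serious deterioration: "many subjects are likely to progress to end organ failure resulting in Intensive Therapy Unit (ITU) admission or death". It then says "Admission to ITU is therefore expected and will not result in withdrawal of the subject". It allows subjects to leave the study at any time, and adds "If the subject loses capacity, the clinician in charge of their care can elect to withdraw the subject", provided that the clinician judges this clinically appropriate. The power is discretionary and conditional. The section does not say whether the subject is withdrawn from treatment or from the study, and does not mention samples or follow-up after the decision. For consent of participants lacking capacity it refers to 4.3 and 8.2.

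**Protocol 4.3** says that patients "will be asked to record their advance wishes regarding continuing enrolment on the consent form".

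**Protocol 8.2** deals with a clinician who gives alternative treatment: "In these cases the participants remain within the study for the purposes of follow-up and data analysis". It also says "All participants are free to withdraw at any time from the protocol treatment without giving reasons", so there withdrawal is from treatment.

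**SAP 2.5** says "Patients withdrawn from the study will still be included in the final analysis". Its reasons for withdrawal include a decision by the PI but not one by the treating clinician.

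**SAP 2.2** restricts the Full Analysis Set (FAS) to patients who received the full course. Those with under 3 days of infusion form the Incomplete Analysis Set (IAS), which gets descriptive statistics only. **SAP 2.4** excludes imputation of the primary endpoint, the change in D-dimer from Day 1 to Day 3.

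**The concern.** Protocol 1.1 links an early rise in D-dimer to death, and 4.4 expects many patients to deteriorate. Capacity may be lost in the course of that deterioration. A withdrawal rule that starts from loss of capacity can therefore remove patients whose D-dimer is behaving differently from everyone else's.

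If withdrawal also ends data collection, the Day 3 value is lost for anyone withdrawn before it. The Day 5 and Day 8 samples, the SOFA components and possibly Day 30 status are lost for anyone withdrawn before those dates. Data missing for this reason cannot be assumed to be missing at random, and the plan has no method for handling them.

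The loss may also be hard to see. SAP Table 2 attributes missed doses only to discharge or death. SAP Table 9 has rows for alive, dead and lost to follow-up, but none for withdrawn.

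**Working it through.** **1. The plan's own figure.** Protocol 7 states 80% power at alpha 0.05 with 30 per group for a 30% change in D-dimer. It gives no SD, scale, sidedness or allowance for loss, so the figure can be neither reproduced nor refuted. The SD of log change that would make it true for a 30% reduction is:

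- two-sided: |ln 0.7| / [(1.960 + 0.842) × √(2/30)] = 0.357 / 0.723 = 0.493
- one-sided: 0.357 / [(1.645 + 0.842) × √(2/30)] = 0.357 / 0.642 = 0.556

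The total is 60, so every patient without a Day 3 value comes off the 30 per arm.

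**2. What the documents do with each kind of patient.**

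- *Given alternative treatment by the clinician:* stays in follow-up and analysis (Protocol 8.2).
- *Infusion stopped early:* advised to stay in hospital for 24 hours while study assessments continue (Protocol 3).
- *Loses capacity and is withdrawn under 4.4 before Day 3:* nothing is said about later samples. If none is taken there is no primary value and none is imputed (SAP 2.4). SAP 2.5 includes the patient; SAP 2.2 gives descriptive statistics only.
- *The same, but a Day 3 sample is obtained:* the value exists, yet with under 3 days of infusion the patient is in the IAS and outside the primary comparison.
- *Withdrawn after Day 3:* the primary value exists, but Day 5 and 8 samples, SOFA and Day 30 status may not. FAS membership depends on whether the full course means the 7 days of Protocol 3 or the 72 hours that SAP 3.5 counts as 100% for the primary endpoint.

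So 4.4 decides whether data exist, and SAP 2.2 decides whether a Day 3 value is used.

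**3. Can the bias be signed or sized?** Suppose, as an assumption, that the fraction q of each arm with the largest rises is lost, and take SD 0.493. The mean log change of those remaining shifts by −SD × φ(z)/(1 − q), where z is the upper-q normal quantile.

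- q = 10%: −0.493 × 0.1755/0.90 = −0.096
- q = 20%: −0.493 × 0.2800/0.80 = −0.173

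The bias in the TRV027-minus-placebo log difference is the TRV027 shift less the placebo shift.

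| Assumed loss, placebo v TRV027 | Bias (log) | Multiplies the treatment ratio by |
|---|---|---|
| 10% v 10% | 0 | 1.000 |
| 20% v 10% | +0.076 | 1.079 (against TRV027) |
| 10% v 20% | −0.076 | 0.926 (for TRV027) |

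The assumed loss by arm fixes both sign and size, and the documents give no such rate.

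**4. Can the effect on power be signed?** Losing 10% per arm at random leaves 27 and takes power from 80% to 75.7% (normal approximation). Losing the three largest rises per arm instead, with a true 30% reduction, raised the rejection rate in simulation (Mann-Whitney, 4,000 runs) from 75.9% to 81.1%, because removing extremes reduces the spread. With no true effect, the same loss raised it from 5.0% to 7.1%. Power can move either way, so no single figure is defensible.

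**The case against.** The strongest case for leaving 4.4 alone has five parts.

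- *The power is conditional.* A reader might infer that any patient who loses capacity can be removed automatically. The text does not support that: a clinical judgement is required, and ITU admission is expressly not a cause of withdrawal. This stands. The remaining fault is that the consequence of the decision for data is undefined.
- *8.2 does not contradict 4.4.* A reader might infer a direct conflict. The retention sentence in 8.2 covers alternative treatment and does not address withdrawal after loss of capacity, so both sections can be followed. This stands: it is a tension, in that a similar clinical judgement keeps the data under one section and may end them under the other.
- *4.4 points to 4.3, where advance wishes are recorded.* It does, for consent. It does not tie the clinician's choice to those wishes.
- *The protocol already separates stopping the infusion from assessment.* Section 3 continues assessments after an early stop, but only through a 24-hour stay, and does not say that this covers a subject withdrawn under 4.4. Day 30 status can come from medical records, but nothing says that this continues after withdrawal.
- *SAP 2.2 is the larger route of loss.* This stands. Patients with under 3 days of infusion are outside the primary comparison whatever 4.4 says.

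Blinding also makes decisions influenced by arm less likely. It does not prevent unequal loss if treatment itself changes who deteriorates.

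**Conclusion.** The point holds as a wording fault with a cheap remedy. Protocol 4.4 permits outcome-related loss of data because it does not separate stopping the infusion from ending data collection. SAP 2.5's promise cannot be met for the primary endpoint when there is no Day 3 value, given SAP 2.4 and 2.2.

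The size and direction are unknown. A reader might infer that the rule dilutes a true effect, hides harm or costs a stated amount of power. The documents support none of these: they give no rate of capacity loss, no rate by arm, no SD and no figure for how D-dimer moves in those withdrawn. The figures in the working are illustrations under assumed rates, and they point both ways. For the primary endpoint, the rule matters only if both loss of capacity and withdrawal come before the Day 3 sample.

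A reader might also infer that amending 4.4 alone would protect the primary result. It would not. It would protect the Day 5 and 8 samples, the SOFA data and the Day 30 survival table. It helps the primary comparison only if SAP 2.2 is reconciled with SAP 2.5.

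**What to change.** 1. **Protocol 4.4.** State that a clinician's decision after loss of capacity does not by itself end data collection. The clinician's freedom over treatment is unchanged, and no view is offered here on when an infusion should stop. Day 3, 5 and 8 results (from scheduled study samples or routine bloods), Day 30 status and safety data continue unless the patient's advance wishes under 4.3, or the consultee, object.
2. **eCRF and reporting.** Record infusion stopped and data collection stopped as separate items, each with date and reason, and report both by arm. Add the treating clinician's decision to the reasons in SAP 2.5.
3. **SAP 2.2 and 2.5.** Reconcile them so that such patients with a Day 3 value enter the primary comparison, and say whether the full course means 7 days or 72 hours. Without this step, the change to 4.4 leaves the primary result as it is.

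The cost is a protocol amendment with ethics notification, possibly a line on the consent and consultee forms (not available for this review), two eCRF fields and a SAP revision. No new procedures are needed.

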5 SAFETY REPORTING

5.1 DEFINITIONS

Adverse Event (AE): any untoward medical occurrence in a patient or clinical study subject that falls within the criteria specified in section 5.2.

Serious Adverse Event (SAE): any untoward and unexpected medical occurrence or effect that:

- **Results in death**
- **Is life-threatening** – *refers to an event in which the subject was at risk of death at the time of the event; it does not refer to an event which hypothetically might have caused death if it were more severe*
- **Requires prolongation of existing inpatients' hospitalisation**
- **Results in persistent or significant disability or incapacity**

- **Is a congenital anomaly or birth defect**

Medical judgement should be exercised in deciding whether an AE is serious in other situations. Important AEs that are not immediately life-threatening or do not result in death or hospitalisation but may jeopardise the subject or may require intervention to prevent one of the other outcomes listed in the definition above, should also be considered serious.

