5.3 SERIOUS ADVERSE EVENTS

All such events, whether expected or not, should be recorded.

An SAE form should be completed and faxed to the Chief Investigator within 24 hours. However, relapse and death due to Covid19, and hospitalisations for elective treatment of a pre-existing condition do not need reporting as SAEs.

All SAEs should be reported to the London South East Research Ethics Committee where in the opinion of the Chief Investigator, the event was:

- 'related', i.e. resulted from the administration of any of the research procedures; and
- 'unexpected', i.e. an event that is not listed in the protocol as an expected occurrence

Reports of related and unexpected SAEs should be submitted within 15 days of the Chief Investigator becoming aware of the event, using the NRES SAE form for non-IMP studies. The Chief Investigator must also notify the Sponsor of all SAEs.

Local investigators should report any SAEs as required by their Local Research Ethics Committee, Sponsor and/or Research & Development Office.

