3.7 Additional data

Vital signs and cardiovascular monitoring will be documented at days 1, 3 and 5. (Table 12).

Table 1. Baseline characteristics

	FAS		IAS	
	Control	TRV027	Control	TRV027
	Median (range) or N (%)			
Age (yr)				
Age group				
<60				
60-69				
>69				
Gender				
Male				
Female				
BMI (kg/m²)				
Ethnicity				
White				
Mixed				
Asian				
Black				
Other				
Disease severity?				
Ie FDA grade 1-5?				

Table 2 Drug Compliance

	Control N (%)	TRV027 N (%)
Total Missed doses		
Total % Compliance		
Median missed doses per patient (range)		
Patients with missed dose due to hospital discharge		
Patients with missed dose due to death		

Table 3 Safety data – Pooled Adverse events

	Control		TRV-027	
	No. of Events	No. of Subjects*	No. of Events	No. of Subjects*
Number of Adverse events				
Severity				
Grade 1				
Grade 2				
Grade 3				
Grade 4				
Grade 5				
Missing				
AE classification				
Not serious				
Serious				
AE expectedness				
Expected				
Unexpected				
Not Applicable				
Missing				
Relation to study				
Definitely				
Probably				
Possibly				
Unlikely				
Not related				
Not assessable				
Missing				

* A patient may have several AEs

Table 4 – TRV027 Safety data –Adverse events details by patient

Control				TRV-027			
Pt ID	AE category	AE name	Grade	Pt ID	AE category	AE name	Grade

Table 6 Safety data – Serious Adverse Events

	Control		TRV027	
	No. of Events	No. of Subjects	No. of Events	No. of Subjects
Number of Serious Adverse Events				
Reasons for SAE				
Resulted in death				
Life threatening				
Congenital anomaly/birth defect				
Persistent or significant				
Disability/incapacity				
Inpatient hospitalisation/prolongation of existing				
Other				
Severity				
Mild				
Moderate				
Severe				
Life threatening				
Death				
Causal relationship to study drug				
Definitely				
Probably				
Possibly				
Unlikely				
Not related				
Not assessable				

Table 7 Safety data – Serious Adverse events details (Controls)

SAE description	SAE Term	Outcome

Table 8 Safety data – Serious Adverse events details (TRV027)

SAE description	SAE Term	Outcome

Table 9 Day 30 Survival

	Control	TRV027
Alive		
Dead		
Lost to follow-up		

Table 10 FAS Efficacy and exploratory parameters

	Control			TRV027		
	Day 1 [N=] Median (range)	Day 3 [N=] Median (range)	Difference D3 – D1	Day 1 [N=] Median (range)	Day 3 [N=] Median (range)	Difference D3 – D1
D-dimer						
Platelets						
aPTT						
INR						
Fibrinogen						

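### Protocol 5.1 makes unexpectedness part of the SAE definition while 5.3 records SAEs regardless of it, so anticipated non-fatal serious events may be counted inconsistently or left out

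*Protocol*

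**What the plan says.** **Protocol 5.1 (Definitions)** defines an SAE as "any untoward and unexpected medical occurrence or effect that" meets one of five criteria: death, threat to life, prolonged hospitalisation, lasting disability, or congenital anomaly. A closing paragraph lets medical judgement class other important adverse events (AEs) as serious, with no mention of expectedness. The AE definition in the same section has no expectedness condition either.

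**Protocol 5.3 (Serious adverse events)** opens with "All such events, whether expected or not, should be recorded". It then exempts some events: "relapse and death due to Covid19, and hospitalisations for elective treatment of a pre-existing condition do not need reporting as SAEs". Ethics committee reports are limited to SAEs that are both related and unexpected, the latter explained as "unexpected', i.e. an event that is not listed in the protocol as an expected occurrence". Finally, "The Chief Investigator must also notify the Sponsor of all SAEs".

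**Protocol 4.4 (Withdrawal criteria)** says that "many subjects are likely to progress to end organ failure resulting in Intensive Therapy Unit (ITU) admission or death", and continues: "Admission to ITU is therefore expected and will not result in withdrawal of the subject".

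**SAP 3.4 and its tables.** Table 3 pools AEs and has a block headed "AE expectedness" beside a serious/not serious split. Table 6 counts SAEs by reason, severity and causal relationship, with no split by expectedness.

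**The concern.** An investigator classifies an event before deciding what to report. Under 5.1 as written, an anticipated event fails the definition however serious it is. The 24-hour form and the sponsor notification in 5.3 apply only to events that have already been classed as SAEs. Under 5.3, the same event is to be recorded. Two sites could each follow the protocol and count the same event differently.

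The events exposed to this are the ones the protocol itself foresees: non-fatal organ failure and deterioration needing intensive care. They are also events in which a harm of the study drug could show. At stake are the between-arm SAE comparison in SAP Table 6, the serious rows of Table 3, and the safety data on which the DSMC advises after every 12 patients. With equal allocation, the first review rests on about 12 / 2 = 6 patients per arm, so the classification of one or two events can change the picture.

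**Working it through.** The documents give no SAE, organ failure or intensive care rate, and no figure in the plan depends on the definition. There is nothing to recompute, so the check is a comparison of the texts.

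1. **Can an SAE be expected?** Under 5.1, no: unexpectedness is a condition of entry. Under 5.3, yes: recording is independent of expectedness.

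2. **What does the ethics filter imply?** Section 5.3 sends to the committee only those SAEs that are related and unexpected. If every SAE were already unexpected, the second condition would do nothing. It has a purpose only if expected SAEs exist.

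3. **What does the SAP assume?** Table 3 provides for both expected and unexpected events and for both serious and non-serious ones. Expectedness there describes an event and does not decide whether it is counted. On this point 5.1 is the outlier.

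4. **Which events are exposed?** Section 5.3 ties unexpectedness to whether the protocol lists the event as an expected occurrence. Section 4.4 calls intensive care admission expected and organ failure likely. Read with 5.1, this gives a site a textual basis for not classing such deterioration as an SAE. The exemption in 5.3 does not mention organ failure or intensive care admission, so 5.3 on its own points to recording them where they meet a seriousness criterion.

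5. **Would the event be caught as an AE instead?** Possibly. Section 5.2 records clinically significant events whether expected or not, and such an event could appear in Table 3 as non-serious. But 5.2 also says that known COVID-19 symptoms are normally not treated as clinically significant, and it keeps creatinine, bilirubin, platelets and troponin out of AE recording because they are endpoints. Those values are where much organ failure would show, so this fallback is weak.

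6. **Would the effect differ by arm?** The study is double-blind, so classification should not depend on treatment. Blinding does not restore uncounted events. The protocol also foresees several NHS Trusts and describes randomisation blocked on age, with no mention of site, so differences in practice between sites need not balance out in a 60-patient trial.

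7. **Does intensive care admission count once the definition rests on seriousness?** Still not clear. It is not one of the five listed criteria, although it may often coincide with a threat to life or a longer stay. The edit to 5.1 alone would not settle this.

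**The case against.** The strongest reply is that the documents, read as a whole, point towards recording expected SAEs. Section 5.3 addresses expectedness directly, its ethics filter presupposes expected SAEs, and SAP Table 3 has a row for them. The reference in 5.3 back to such events can be read as meaning those that meet the seriousness criteria. This stands as an account of the probable intent. It does not remove the contradiction, because nothing in the protocol says that 5.3 overrides 5.1.

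Several stronger conclusions are tempting, and the documents do not support them:

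- *A reader might infer that expected serious events certainly fall outside the safety counts.* That needs every site to apply 5.1 and disregard 5.3.
- *A reader might infer that the count of serious expected events must be zero in both arms.* The closing paragraph of 5.1 gives a route to seriousness without an expectedness condition, so this fails even on a literal reading. That route does not cover every event.
- *A reader might infer that these events would be absent from Table 3.* They may still enter as AEs through 5.2, subject to its carve-outs.
- *A reader might infer that the DSMC could not see an excess.* Protocol 5.4 has it review the endpoints as well. Sequential organ failure score, coma score, inotrope requirement and organ-function laboratory values are scheduled on days 1, 3, 5 and 8.
- *A reader might infer that deaths are hidden by the wording of 5.1.* Survival to day 30 is tabulated by arm in SAP Table 9. The exclusion of COVID-19 deaths from SAE reporting comes from the explicit exemption in 5.3, which is a separate matter.

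It is also fair to say that the word expected in 4.4 stands in a withdrawal rule, not in a list of expected events for safety reporting. The protocol gives no other such list for 5.3 to refer to, so a site could reasonably look there.

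**Conclusion.** The contradiction between Protocol 5.1 and 5.3 is real and lies in a core safety definition. Its supportable consequence is possible omission, or inconsistent counting, of non-fatal serious events that the protocol anticipates. It affects SAP Table 6, the serious rows of Table 3 and the SAE part of what the DSMC sees.

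The size cannot be calculated. It depends on how many such events occur and on how many sites follow 5.1 rather than 5.3, and the documents give neither. The survival table and the DSMC's access to endpoints limit the harm but do not replace a consistent SAE count: SAP Tables 10 and 11 show only days 1 and 3, and laboratory values do not record whether an event was serious or related to the drug. The point should be corrected because it is unambiguous and cheap to correct, not because an undercount has been shown.

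**What to change.** - In Protocol 5.1, delete the words *and unexpected* so that the SAE definition rests on seriousness alone.
- Keep expectedness as an attribute recorded for each event, used for the ethics-reporting condition in 5.3 and for SAP Table 3.
- Reconcile 4.4, 5.1 and 5.3 so that the protocol states whether organ failure and intensive care admission are counted as SAEs, and whether 4.4 is meant to list expected occurrences for the purposes of 5.3.
- Tell sites of the change in a short note, so that events are classified alike throughout.

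The cost is a short protocol edit, the site note and some more SAE forms in a 60-patient trial. No treatment rule changes. The exemption in 5.3 for COVID-19 relapse and death is unaffected and would need its own decision.
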